## 9.2 Adverse event and device deficiency assessment

### 9.2.1 Adverse Events

To ensure that all AEs which are potentially relevant are collected, all system related, procedure related, cardiovascular related and serious AEs will be collected throughout the study duration, starting at the time of signing the consent form. Reporting of these events to Medtronic will occur on an AE form, including a description of the AE, date of AE onset, treatment, resolution, and assessment of both the seriousness and the relatedness to the device.

Exceptions include:

- Documented pre-existing conditions are not considered AEs unless the nature or severity of the condition has worsened
- Recurrence of AF event unless an invasive action was taken
- Unavoidable AEs unless the AE worsens or is present outside the stated timeframe listed in Table 8

For AEs that require immediate reporting (see Table 9: Adverse Event Reporting), initial reporting may be done by phone, fax, email or on the CRF completing as much information as possible. The completed AE CRF must be submitted to Medtronic as soon as possible. Each AE must be recorded on a separate AE Form. Subject deaths are also required to be reported. Refer to Section 9.5 for Subject Death collection and reporting requirements.

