#### **6.9 Randomization**

Randomization schedules will be prepared for each site using a random permuted block design stratified by center and AF diagnosis. The schedules will allocate subjects in a 1:1 ratio to the treatment or control arm.

Each center will receive a set of sequentially numbered envelopes labeled specifically for that center that is labeled with one randomization code per envelope. After a CT scan has been performed and confirmed that the renal anatomy meets eligibility requirements, the subject will be randomized.

The next sequential envelope labeled with a randomization code will be used. The envelope number will be recorded for each randomized subject and communicated to Medtronic. The sequence of subject randomization will be checked to ensure it matches the sequence of envelope numbers.

Randomization assignments are the following:

- Treatment:
  - Perform the pulmonary vein isolation procedure, renal angiogram, renal artery denervation procedure and the Reveal LINQ insertion.
- Control:

- Perform the pulmonary vein isolation procedure and the Reveal LINQ insertion. Do NOT perform renal denervation.

Enrolled subjects who were not randomized should be exited. See Section 9.2.2 if the subject has an ongoing adverse event.

Subjects and center personnel will be blinded to the randomization assignment until after the pulmonary vein isolation procedure.

Crossing over to the Treatment group once assigned to the Control group is not allowed at any point during the study.

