### **6.19 Unscheduled follow-up visits**

An unscheduled visit is defined as any study-related visit which does not occur within the designated visit window of a scheduled follow up visit. Subjects who are seen outside of their regularly scheduled follow up visit for arrhythmia symptoms or suspected symptoms associated with renal denervation should have unscheduled procedures and data collection completed.

The following will be collected:

- blood and urine samples (optional)
- physical exam
- vital signs (including 3 blood pressure measurements according to Appendix G: Blood Pressure Measurement Procedures)
- review of medications
- assess for adverse events
- assess arrhythmias and symptoms, episodes of medical care suggestive of arrhythmia including hospitalizations, office or ER visits, or any AF-related procedures such as cardioversions or additional ablations
- interrogate the Reveal LINQ device, review prior CareLink reports and the current interrogation for possible AF related events

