## 9.1 Adverse event and device deficiency definitions

Where the definition indicates “device”, it refers to any device used in the study. This might be the devices under investigation or any market released component of the two systems.

For the purpose of this study, all Adverse Events (AEs) and Device Deficiencies (DDs) will be classified according to ISO 14155:2011.

Table 8: Adverse event definitions

General	
Adverse Event (AE)	
Any untoward medical occurrence, unintended disease or injury, or untoward clinical signs (including abnormal laboratory findings) in subjects whether or not related to the investigational medical device. (ISO 14155:2011 3.2)
 
NOTE 1: This definition includes events related to the investigational medical device or the comparator.
 
NOTE 2: This definition includes events related to the procedures involved.
 
NOTE 3: For users or other persons, this definition is restricted to events related to investigational medical devices.

Adverse Device Effect (ADE)	
Adverse event related to the use of a medical device (ISO 14155:2011 3.1)
 
Note 1: This definition includes adverse events resulting from insufficient or inadequate instructions for use, deployment, implantation, installation, or operation, or any malfunction of the medical device.
 
Note 2: This definition includes any event resulting from an error use or from intentional misuse of the medical device.

Hospitalization	A hospital admission lasting more than 24 hours or which includes an overnight admission.
Relatedness	
Procedure related	
An adverse event that occurs due to any portion of the cryoablation or renal denervation procedures related to the study.
 
Cryoablation procedure related: event is related to any portion of the procedure that encompasses cryoablation.
 
Renal angiogram: event is related to any portion of the procedure that encompasses the renal angiogram.
 
Renal denervation procedure related: event is related to any portion of the procedure that encompasses renal denervation.
 
Reveal LINQ insertion procedure related: event is related to any portion of the procedure that encompasses insertion of the Reveal LINQ device.
 
Procedure related: if it cannot be determined which portion of the procedure an event is related to.

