System related	
Cryoablation system related: event that results from the presence or performance (intended or otherwise) of the cryoablation system.
 
Symplicity Renal Denervation system related: event that results from the presence or performance (intended or otherwise) of the Symplicity Renal Denervation system (Symplicity Spyral Catheter and Symplicity G3 Generator).
 
Reveal LINQ system related: event that results from the presence or performance (intended or otherwise) of the Reveal LINQ device.
 
Other system related: An adverse event that results from the presence or performance (intended or otherwise) of any device/tool used not related to the cryoablation, renal angiogram, renal denervation procedure or Reveal LINQ system.

Cardiovascular related	An adverse event relating to the heart and the blood vessels or circulation.
Seriousness	
Unanticipated Adverse Device Effect (UADE)	Any serious adverse effect on health or safety or any life-threatening problem or death caused by, or associated with, an (investigational) device, if that effect, problem, or death was not previously identified in nature, severity, or degree of incidence in the CIP or applicable (including a supplementary plan or application), or any other unanticipated serious problem associated with a device that relates to the rights, safety, or welfare of subjects. (21 CFR 812.3(s))
Serious Adverse Event (SAE)	
Adverse event that
 
a) led to death,
 
b) led to serious deterioration in the health of the subject, that either resulted in
 
 
• a life-threatening illness or injury, or
 
• a permanent impairment of a body structure or a body function, or
 
• in-patient or prolonged hospitalization, or
 
• medical or surgical intervention to prevent life-threatening illness or injury or permanent impairment to a body structure or a body function,
 
 
b) led to fetal distress, fetal death or a congenital abnormality or birth defect (ISO 14155:2011 3.37)
 
NOTE: Planned hospitalization for a pre-existing condition, or a procedure required by the CIP, without serious deterioration in health, is not considered a serious adverse event.

Serious Adverse Device Effect (SADE)	Adverse device effect that has resulted in any of the consequences characteristic of a serious adverse event. (ISO 14155:2011 3.36)

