## 9.7 Adverse event classification

All reported adverse events and device deficiencies will be reviewed by a Medtronic representative. AEs will be classified according to the definitions provided.

Upon receipt of adverse events at Medtronic, a Medtronic representative will review the adverse event/device deficiency for completeness and accuracy and when necessary will request clarification and/or additional information from the Investigator. Medtronic will utilize MedDRA, the Medical Dictionary for Regulatory Activities, to assign a MedDRA term for each adverse event based on the information provided by the investigator.

Adverse Events and Deaths will be classified according to the standard definitions as outlined below:

Table 10: Adverse event and subject death classification responsibilities

What is classified?	Who classifies?	Classification Parameters
Timing of the Event	Investigator	Pre-procedure, cryo-procedure, renal denervation-procedure, assessment, post-procedure
Relatedness	Investigator	Symplicity System, Arctic Front Cardiac Cryoablation System, renal artery denervation procedure, cryoablation procedure, Reveal LINQ system and procedure other procedures
	Sponsor	Same as Investigator
Severity	Investigator	SAE
	Sponsor	SAE, UADE, Complication or Observation (for all system or procedure related adverse events)
Diagnosis	Investigator	Based on presenting signs and symptoms and other supporting data
	Sponsor	MedDRA term assigned based on the data provided by investigator
Death Classification 	Investigator	Cardiac, Sudden Cardiac, Non-sudden Cardiac, Non-Cardiac, Unknown

 Deaths will only be adjudicated to death classification. All other adjudications information will be taken from the corresponding AE with an outcome of death

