There are additional risks that could possibly be associated with the denervation procedure/therapy. These potential risks have not yet been quantified, but may include:

- Pain-discomfort that can range from mild to severe that may occur peri- and/or post-procedure.
- Damage to one or both kidneys and/or loss of kidney function-perforation of kidney or an occlusion or blood flow to the kidney (e.g. from stenosis or embolism) and/or reduction of glomerular filtration rate. If severe enough, this could require dialysis.
- Renal artery aneurysm-localized weakening and ballooning of the renal artery from the interventional procedure or the delivery of RF energy.
- Renal artery stenosis-narrowing of the renal artery due to the interventional procedure or the delivery of RF energy.
- Arterial spasm or constriction-acute or chronic narrowing of the renal artery lumen diameter at denervation locations due to arterial muscle contraction, local tissue contraction or local edema.
- Thermal injury to the vasculature or other structure from energy application- damage to an artery, vein or other structure due to the delivery of RF energy.
- Hypertension-worsening high blood pressure.
- Hypotension-low blood pressure. Blood pressure reduction may occur too far and/or too quickly and may cause end organ hypoperfusion.
- Orthostatic hypotension-temporary reduction of blood pressure when going from lying to standing, coupled with symptoms (e.g. dizziness, light headedness).
- Hematuria-blood in urine.
- Hemorrhage-significant blood loss.
- Proteinuria-elevated levels of protein in urine.
- Electrolyte disturbances-an imbalance of the electrolytes (sodium, potassium).
- Skin burn-damage to the skin caused by energy conduction via the ground pad used with the Symplicity Renal Denervation system (Symplicity Spyral Catheter and Symplicity G3 Generator).

There are additional risks that could possibly be associated with the Reveal LINQ.

- Rejection of the Reveal LINQ by your body, which may involve symptoms such as swelling, redness, or other irritation at, or near, the implant site.
- Movement of the Reveal LINQ from its initial position or coming through the skin.

- Infection at the site of the implant.
- Over-sensing or under-sensing (incorrectly identifying too many or too few) times where your heart may be showing a rhythm problem.

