6.0	6.7	Added a CT scan to screen for renal anatomy eligibility followed directly by randomization rather than screening for renal anatomy directly after the pulmonary vein isolation procedure.	Allows for more efficiency with planning of the renal denervation procedure.	0

Version	Applicable Sections	Change	Rationale	Number of subject enrolled
6.0	6.7, 6.17, 12.6	Changed trans-thoracic echocardiogram measurement to only left atrial volume index for subjects diagnosed persistent AF.  The repeat trans-thoracic echocardiogram at 6 months was removed	Want to exclude subjects who are very far along the AF disease continuum so that the two groups, paroxysmal and persistent aren't too dissimilar  Likelihood of seeing a meaningful difference six months post procedure did not warrant this objective	0
6.0	6.7, 6.17, 12.6	Removed quality of life questionnaire	Likelihood of seeing a meaningful difference six months post procedure did not warrant this objective	0
6.0	5.2.1, 6.7, 6.17, 12.6	Removed ambulatory blood pressure monitoring requirement and follow up visit measurements	Deemed not critical for this study based on HTN-3 results	0
6.0	6.14	Changed the definition of device deficiency	New information	0
6.0	6.17	Removed the 3 month follow up visit	Primary reason for the 3 month follow up visit was to address any potential safety issues with the renal artery denervation procedure, risk level has been lowered with recent results from the Symplicity HTN-3 study	0
6.0	6.18	Included System Modification instructions for the Reveal LINQ device	New information	0
6.0	6.20	Clarified criteria for permissible retreatments	Unnecessary restriction in this feasibility study	0
6.0	7	Added instructions for device disposition with the Arctic Front Advance catheter	Result of including the persistent AF population in the study	0
6.0	9	Clarified that only system related, procedure related, cardiovascular related and serious AEs will be collected rather than all AEs	Safety risk level has been lowered with recent results from the Symplicity HTN-3 study	0
6.0	9	Changed Adverse Events Adjudication Committee (AEAC) to Clinical Events Committee (CEC)	Clarification because the committee will review more than adverse events	0
6.0	9.1	Added chest pain to the unavoidable AE table	Reasonable expectation of occurrence	0

Version	Applicable Sections	Change	Rationale	Number of subject enrolled
6.0	9.3	Elaborated market-release reporting requirements	Clarification	0

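### Non-serious hematuria, electrolyte disturbance, non-vascular pain and renal AE entries are recorded only if judged study-related by staff who know the arm, so capture is likely to differ between Treatment and Control

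*Protocol*

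**What the plan says.** - **Collection rule.** CIP 9.2.1 says "all system related, procedure related, cardiovascular related and serious AEs will be collected throughout the study duration", starting at consent. Exceptions cover unchanged pre-existing conditions, AF recurrence without invasive action, and unavoidable procedural events within the Table 8 timeframes.
- **Who attributes, and what they know.** CIP 6.9: "Subjects and center personnel will be blinded to the randomization assignment until after the pulmonary vein isolation procedure". No later blinding of site staff is described. In CIP 9.7, Table 10, the investigator and then the sponsor classify relatedness, against categories that begin "Symplicity System, Arctic Front Cardiac Cryoablation System, renal artery denervation procedure, cryoablation procedure". CIP 9.6 makes blinding of the Clinical Events Committee optional.
- **Routes open to both arms.** In CIP 9.1, Table 8, cryoablation-procedure related means "event is related to any portion of the procedure that encompasses cryoablation". Cardiovascular related means "An adverse event relating to the heart and the blood vessels or circulation", with no attribution to the study required.
- **Listed risks.** CIP section 10 introduces the denervation risks with "These potential risks have not yet been quantified, but may include". The list includes pain, loss of kidney function, hematuria, proteinuria and electrolyte disturbance, alongside vascular and blood-pressure risks.
- **Unscheduled visits.** CIP 6.19 says that subjects seen out of window for "arrhythmia symptoms or suspected symptoms associated with renal denervation should have unscheduled procedures and data collection completed".
- **Reporting.** SAP 7.11 tabulates AEs for the enrolled set. The columns of its example table are not randomized, randomized and enrolled; there is no split by arm.

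**The concern.** The study exists to characterise what adding denervation does to safety, and the CIP itself says that these risks are unquantified. For an event that is neither serious nor cardiovascular, the decision to record it is the attribution decision. After the ablation that decision is made with the arm known. A Treatment subject offers three extra things to attribute an event to: the renal angiogram, the denervation procedure and the denervation system. A Control subject with the same finding two months after the procedure has only the ablation, the cardiac monitor and the generic categories.

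Hematuria is the clearest case. CIP 6.11 has heparin given during ablation in both arms, and CIP 6.16 recommends systemic anticoagulation for at least two months afterwards. Some background bleeding is plausible in both arms, and a Treatment count cannot be read without a Control count collected by the same rule. An event that never reaches the AE form cannot be recovered by any later analysis, and the events committee reviews only what was reported.

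**Working it through.** No figure in the plan depends on this rule, so there is none to reproduce. The check sorts the listed denervation risks by their route into the database, then illustrates the effect.

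**Step 1: sort the risks in CIP section 10 by route.**

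| Listed risk, non-serious | Route under 9.2.1 | Arm-neutral? |
|---|---|---|
| Renal artery stenosis, aneurysm, arterial spasm | Cardiovascular | Yes |
| Hypertension, hypotension, orthostatic hypotension, hemorrhage | Cardiovascular | Yes |
| Proteinuria, reduced kidney function | AE form needs attribution; laboratory value is scheduled | AE entry no, value yes |
| Hematuria | Needs attribution | No |
| Electrolyte disturbance | Needs attribution | No |
| Non-vascular pain | Needs attribution | No |

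Serious forms of all of these are collected in both arms.

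**Step 2: look for an arm-neutral backup.** Serum creatinine, urine albumin/creatinine and cystatin C are scheduled without arm restriction at baseline (CIP 6.8), discharge (6.16), and 1 and 6 months (6.18.1). Hematuria and electrolytes are not in that panel (Table 5). The SAP names laboratory results only among baseline characteristics (7.6) and plans no by-arm follow-up summary.

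**Step 3: illustrate the size.** Incidence and capture below are assumptions, not document figures. With 70 subjects randomized 1:1, n = 70/2 = 35 per arm.

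- Expected recorded count = 35 × true incidence × capture probability.
- Spurious difference = true incidence × (Treatment capture − Control capture).
- True incidence is the same in both arms, and Treatment capture is 0.9.
- The last column is the exact probability that a two-sided Fisher test gives p < 0.05.

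| True incidence | Control capture | Recorded, Treatment vs Control | Spurious difference (points) | P(Fisher p < 0.05) |
|---|---|---|---|---|
| 10% | 0.9 | 3.2 vs 3.2 | 0 | 1.1% |
| 10% | 0.5 | 3.2 vs 1.8 | 4.0 | 2.0% |
| 10% | 0.25 | 3.2 vs 0.9 | 6.5 | 4.2% |
| 10% | 0.1 | 3.2 vs 0.4 | 8.0 | 6.6% |
| 20% | 0.9 | 6.3 vs 6.3 | 0 | 2.4% |
| 20% | 0.5 | 6.3 vs 3.5 | 8.0 | 8.7% |
| 20% | 0.25 | 6.3 vs 1.8 | 13.0 | 24.3% |
| 20% | 0.1 | 6.3 vs 0.7 | 16.0 | 42.9% |

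For example, 0.20 × (0.90 − 0.25) = 0.13. If capture is low in both arms, say 40–60% in Treatment and 10–20% in Control, the recorded rates differ by a factor of 0.4/0.2 = 2 to 0.6/0.1 = 6 with no true effect. In that range Treatment also loses 40–60% of its events. The rows with equal capture show what an arm-neutral rule achieves: no expected difference.

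**The case against.** The strongest case against is that little is exposed and the comparison at risk is not planned.

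- **The restriction is deliberate.** Appendix I, version 6.0, records: "Clarified that only system related, procedure related, cardiovascular related and serious AEs will be collected rather than all AEs". The reason given is the reassuring safety result of Symplicity HTN-3. This is a feasibility study with no safety hypothesis (CIP 12.3.2). That stands as an explanation. It does not settle the matter, because CIP 12.3.4 says that those results came from the first-generation catheter and G2 generator, whereas this study combines Spyral and G3 with cryoablation.
- **Control has routes in.** Besides cryoablation and the cardiac monitor, Table 8 has a generic procedure category for when the portion cannot be determined and an other-system category. Table 10 includes other procedures. Control subjects also receive contrast, so contrast nephropathy is reportable. This stands: Control capture is lower in expectation, not zero.
- **No by-arm AE table or test is specified.** This also stands. The formal arm comparison of safety is the serious composite. But a reader of a randomized safety study will want these events by arm, and the data would not support it.
- **Any bias runs against the sponsor's own device.** True on the natural assumption that attribution is likelier in Treatment. It would still misinform the design of a pivotal study.

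A reader might infer that CIP 6.19 orders extra visits in Treatment. It does not. It says what to collect when a subject is seen out of window, unscheduled visits are defined for either arm, and AEs are assessed at every scheduled visit in both. The only defect there is a symptom phrase that can hardly apply to Control.

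**Conclusion.** The point holds in a narrow form, as a worthwhile and cheap improvement. For non-serious hematuria, electrolyte disturbance and non-vascular flank or abdominal pain, and for AE-form entries of proteinuria or reduced renal function, recording depends on an attribution made with the arm known, and nothing else in the plan repairs it. Hematuria and electrolyte disturbance are the most exposed, since the scheduled panel does not measure them. The effect is confined to descriptive AE tables. Its direction, an apparent excess in Treatment, rests on the assumption that staff attribute such events more readily where denervation was performed.

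Two stronger readings are tempting, and the documents do not support them. One is that denervation's listed renal risks as a whole are lost in Control. The renal artery and blood-pressure risks enter as cardiovascular events in both arms, and kidney function and albuminuria are measured on the same schedule in both to 6 months. The other is that the primary safety conclusion is compromised. The composite in CIP 12.3 counts only serious events, which are collected whatever their relatedness. The documents give neither incidence nor capture rates, so no figure for the Control loss can be derived; the figures above only show a possible range.

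**What to change.** - **CIP 9.2.1:** add that non-serious renal and urinary AEs, electrolyte disturbance, and flank or abdominal pain are collected in both arms from the procedure to the 6-month visit, regardless of relatedness. Keep the existing unavoidable-AE exceptions.
- **CIP 6.19:** reword the symptom phrase so that it names symptoms and applies to all randomized subjects.
- **SAP 7.11:** tabulate these terms by randomized arm regardless of relatedness. Add a by-arm summary of eGFR, cystatin C and urine albumin/creatinine ratio at discharge, 1 and 6 months.

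The cost is a few added sentences, two tables and a modest number of extra AE forms, mainly in Control. No scheduled visit or test is added. The arm-neutral wording in 6.19 may bring some additional Control subjects under the unscheduled data collection.

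The limit is timing. Appendix I shows 100 subjects enrolled by version 18.0, and a prospective change does not recover events that went unrecorded before it. The report should say which subjects were followed under which rule. The laboratory summary has no such limit, because it uses values already scheduled for everyone.

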Unavoidable Adverse Event	An Adverse Event inherent to a surgical procedure that is expected to occur in all subjects for a projected duration according to the Investigator's opinion, including, but not limited to those provided below. These are not reportable AEs unless they occur after or last longer than the timeframe. If any other events below are classified as serious they must be reported as an adverse event.

Event Description	Timeframe (hours) from the Surgical Procedure
Anesthesia related nausea / vomiting	24
Low-grade fever (<100°F or 37.8°C)	48
Incisional pain	72
Mild to moderate bruising / ecchymosis	168
Sleep problems (insomnia)	72
Back pain related to laying on table	72
Shoulder/arm/leg pain/discomfort/stiffness related to immobilization during procedure	72

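### The exception for AF recurrence in CIP 9.2.1 has no seriousness clause, so an admission for recurrent AF that meets the SAE definition need not reach the SAE data

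*Protocol*

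**What the plan says.** CIP 9.2.1 sets the collection rule: "all system related, procedure related, cardiovascular related and serious AEs will be collected throughout the study duration", starting at consent. Exceptions follow in the same section. Three matter here:

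- AF recurrence: "Recurrence of AF event unless an invasive action was taken".
- Pre-existing conditions: "Documented pre-existing conditions are not considered AEs unless the nature or severity of the condition has worsened".
- Unavoidable events, within the time limits of Table 8. For these, Table 8 adds: "If any other events below are classified as serious they must be reported as an adverse event".

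The section also says: "Subject deaths are also required to be reported".

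Table 8 (CIP 9.1) defines hospitalization as "A hospital admission lasting more than 24 hours or which includes an overnight admission". Its SAE definition covers serious deterioration in health that results in, among other outcomes, "in-patient or prolonged hospitalization". A note removes from the SAE category "Planned hospitalization for a pre-existing condition, or a procedure required by the CIP, without serious deterioration in health".

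SAP 7.11 tabulates reported AEs, including SAEs, for the enrolled analysis set.

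**The concern.** Every subject has AF, and recurrence is the outcome the trial expects to be common. An exception for recurrence is reasonable for routine episodes, which the effectiveness endpoint captures. This one turns on how the episode was managed, not on how serious it was. A subject who deteriorates and is admitted unexpectedly with AF, but has no invasive action, falls on the exempt side.

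What is at stake is the completeness of the serious-event record in a feasibility study of 70 randomized subjects, where a few events change a descriptive table. If denervation affects AF, the omitted events could also differ between arms, so any by-arm SAE comparison could be affected unequally.

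**Working it through.** The plan states no figure on this point. The check is mainly of the text, with one illustration of scale.

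**1. Is there an event that is an SAE but exempt?** Take an unplanned overnight admission for recurrent AF with serious deterioration and no invasive action.

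- It is a hospitalization under Table 8.
- It meets the SAE definition, because serious deterioration led to in-patient care. The note on planned admissions does not apply.
- The AF bullet in 9.2.1 exempts it.

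So such an event exists under the literal text.

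**2. How do the exceptions compare?**

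| Exception | What brings the event back into reporting | Is seriousness enough? |
|---|---|---|
| Unavoidable events | Worsening, exceeding the time limit, or being serious (Table 8) | Yes |
| Pre-existing conditions | Worsening in nature or severity | Not named, but worsening is enough |
| AF recurrence | Invasive action | No, except death |

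AF pre-exists in every subject, so for worsened AF the second and third rows point in opposite directions.

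**3. Is invasive action defined?** No. Table 8 defines only noninvasive, and only for a diagnostic device or procedure. That does not classify a therapeutic act such as electrical cardioversion in either direction, so each site must decide.

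**4. Does another planned analysis recover the event?**

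- Safety composite: the arrhythmia component excludes AF (CIP 12.3.1.9).
- Effectiveness endpoint: AF in the first 90 days does not count. After that it counts LINQ-recorded AF or an AF intervention and excludes cardioversion (CIP 12.4). A later recurrence may count as a failure, but the admission does not register.
- AF burden: starts at day 91 (SAP 7.10.9.3) and measures time in AF.
- Visits and exit: sites ask about arrhythmia hospitalizations (CIP 6.18.1, 6.19, 6.24), but no analysis in the SAP text available uses the answers.

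The gap is widest in days 0 to 90, which neither the effectiveness endpoint nor AF burden covers.

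**5. Scale.** Inputs: 70 subjects randomized 1:1, so 35 per arm; 6-month success of 50% in Control and 75% in Treatment (CIP 12.4.6). Attrition is ignored.

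- Control failures: 35 × 0.50 = 17.5
- Treatment failures: 35 × 0.25 = 8.75
- Total: 26.25

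The share of failures leading to a qualifying admission is not in the documents and is assumed:

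| Assumed share | Control | Treatment | Total omitted |
|---|---|---|---|
| 1% | 17.5 × 0.01 = 0.18 | 8.75 × 0.01 = 0.09 | 0.26 |
| 5% | 17.5 × 0.05 = 0.88 | 8.75 × 0.05 = 0.44 | 1.31 |
| 20% | 17.5 × 0.20 = 3.50 | 8.75 × 0.20 = 1.75 | 5.25 |

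The 2:1 split between arms follows from the design effect (17.5 / 8.75 = 2). With no treatment effect the expected omissions would be equal. Failures exclude days 0 to 90 by definition, so admissions in that period would add to these totals.

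**The case against.** The strongest reply is that this is an open choice. The exception stands in the same section as the collection rule, and AF recurrence is the effectiveness outcome, so keeping it off AE forms is deliberate. That stands: a reader might infer that the CIP breaks a promise to collect every SAE, and it does not.

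Other limits also stand:

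- A reader might infer that every overnight stay for AF is a lost SAE. Serious deterioration is required, and planned admissions without it are excluded.
- A reader might infer that Table 8 makes cardioversion noninvasive. Its wording concerns diagnostic devices and procedures.
- Deaths are always reported. A distinct serious event, such as a stroke, is not a recurrence of AF and is not exempted by the bullet.
- The pre-existing-condition bullet could be read as keeping worsened AF reportable. This makes the text ambiguous; it does not close the gap.
- The example table in SAP 7.11 has columns for not randomized, randomized and enrolled subjects, and none by arm. The SAP says the final version may differ. The documents therefore do not show that a planned by-arm SAE comparison would be distorted.
- Many LINQ-detected failures may be brief and never prompt care, so a low admission share is plausible.
- The SAP does not limit further analyses, so admissions could be tabulated without amending it. Part of the SAP directly after the 7.11 example table was not available, so the absence of such a table cannot be fully confirmed.

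None of this puts the qualifying admission on an AE form.

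**Conclusion.** The point holds as a gap in the reporting rule. Following CIP 9.2.1 as written, a recurrence of AF that meets the SAE definition without death or an invasive action need not be reported, and so would be absent from the SAP 7.11 table.

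The size is uncertain: about 0.3 to 5.3 omitted events by 6 months, resting on the design failure rates and an assumed admission share of 1% to 20%. A reader might infer that the omissions rival the whole safety composite. The rates in CIP 12.3.4 imply 35 × 0.031 + 35 × 0.045 = 2.7 to 35 × 0.031 + 35 × 0.092 = 4.3 composite events. Reaching even the lower figure needs a share of about 10% (2.7 / 26.25), for which the documents give no support.

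A reader might also infer that a primary result is at risk. It is not: AF is outside the composite by definition, and the effectiveness, secondary and ancillary endpoints do not depend on whether an AF admission is reported as an AE. The effect is confined to descriptive serious-event data and any comparison built on them. The change is worth making because it is cheap and removes an inconsistency.

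**What to change.** 1. In CIP 9.2.1, reword the bullet along these lines: *Recurrence of AF, unless it is serious under Table 8 or led to an invasive action.* This aligns it with the treatment of unavoidable events and removes the conflict with the pre-existing-condition bullet for serious cases.
2. Define invasive action in Table 8, stating whether electrical cardioversion counts, so that all sites apply one rule.
3. In the SAP, add a descriptive table of AF-related hospitalizations by arm, from the follow-up and exit information, showing days 0 to 90 separately from later follow-up.

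The cost is one clause, one definition, a few more AE forms and one table. Sites already ask about these hospitalizations. No endpoint, sample size or test changes.
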